#### **6.2.12 Pregnancy**

Subjects who become pregnant will be followed until pregnancy completion and reported as per FDA reporting guidelines.

### 6.2.13 Adverse Events

Adverse Events will be assessed during all On-Study/On-Intervention Evaluation visits.

## 6.3 Special Instructions and Definitions of Evaluations

### 6.3.1 Informed Consent

The subject will be provided and allowed time to review the study informed consent form as outlined in the study Manual of Procedures and as described in section 6.2.1.

### 6.3.2 Documentation of Degree of Inefficient Zone of Keratinized Oral Mucosa

The study subject source documents will document the need for additional zone of keratinized oral mucosa for each subject. We will use a standard trapezoidal graft measuring up to approximately 15 x 10 x 20 mm for both arms of the study.

### 6.3.3 Medical History

The subject Medical and Dental history will be questioned and documented by the subject's recollection of history. Source documentation from hospital records may be collected and reviewed to determine subject eligibility or for inclusion/exclusion criteria.

### 6.3.4 Study Intervention Modifications

Any Study Intervention Modifications must be discussed with the Medical Monitor prior to implementation unless changes are required due to emergency needs of the subject. All modifications must be reported to the Medical Monitor within 24 hours of occurrence if not prior to the event. All study intervention modifications will also need to be reported to the IRB and FDA (if required per 21 CFR 312.30) prior to the change being made unless the change is intended to eliminate an apparent immediate hazard to the subjects.

### 6.3.5 Clinical Assessments

Clinical assessments include width of keratinized mucosa (KM) as determined by the distance between the crest of the edentulous ridge, the gingival margin of the tooth, or the implant mucosal margin and the mucogingival line to the nearest millimeter, graft contracture, graft color as determined by assessing tissue perfusion, postoperative pain, Wound Healing Index (WHI), color of graft tissue compared to surrounding

3/28/2017

non-grafted tissue, and oral care follow-up. These assessments will be performed at post-operative visits 5, 6, 7 and 8. Periodontal measures include Periodontal Pocket Depth (PPD – measured from gingival margin to base of periodontal pocket to nearest millimeter), gingival recession measured from cemento-enamel junction on tooth to gingival margin, Clinical Attachment Level (CAL- determined by subtracting the gingival recession from PPD), and bleeding on probing (BOP) determined as present (1) or absent (0),

Visual analog scale for pain will be assessed for groups, I (at time of harvest of biopsy and EVPOME placement) and group II at time of harvesting of palatal donor graft and grafting at recipient site.

#### 6.3.6 Laboratory Evaluations

Histology and immunohistochemistry evaluations will be performed on tissue collected via the Visit 6 biopsy. Histology will consist of standard hematoxylin and eosin stains to assess presence and maturity of the epithelial layer, while immunohistochemistry will assess the endothelial cells in microvessels within the dermal component.

#### 6.3.7 Intraoral Photographs

Standardized intraoral photographs will be taken at each visit.

#### 6.3.8 X-rays

If a current panoramic radiograph or full mouth series of periapical radiographs are not available, new ones should be obtained. Close proximity of the mental nerve canal, periapical (endodontic) lesions or other pathologies to the anticipated surgical site may contradict surgery. Radiographs taken in the past two years are sufficient to determine if surgery is contradictory.

### 7. MANAGEMENT OF ADVERSE EXPERIENCES

Expected, mild and routine adverse experiences including swelling, bruising, bleeding at the site, numbness at the site, lack of sensation, pain associated with the grafting site and lack of adherence of the graft after stent removal will not be considered adverse events, unless the magnitude or duration is greater than what is routinely expected. These events, however, will be documented in the medical record. If the magnitude or duration is greater than what is routinely expected, the experience will be considered an adverse event and will be recorded on the Case Report Form. Serious, expected and unexpected (serious or not serious) adverse events will be collected at every study visit and recorded on the Case Report Forms.”

Quality Control procedures at the CTML will be in place to reduce the likelihood of EVPOME contamination. Comprehensive post-operative oral care instructions will be

3/28/2017

distributed to study subjects. Adverse events will be reported as described in Section 10.4.

Possible risks to the subjects participating in this study include:

- Pain, swelling, numbness or discomfort from the biopsy of the roof of the mouth
- Contamination of the graft
- Graft failure
- Pain at the surgical site
- Possible unforeseeable harm to pregnant women, the embryo, or fetus
- Allergic reaction to the reagents used in the development of the EVPOME

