6.1 Schedule of Evaluations

Procedure	Visit 1 Screening	Visit 2 Harvest Biopsy	Visit 3 Base- line Intra-oral Graft	Visit 4 Post- Op	Visit 5 Follow-up	Visit 6 Biopsy and Follow-up	Visit 7 Follow-up	Visit 8 End of Study
Timeline (in reference to baseline)	-1 to -90 days	-2 to -40 days	Day 0	Week 1 +/- 3 days	Week 2 +/- 3 days	Week 4 +/- 1 week	Week 8 +/- 1 week	Week 24 +/- 1 week
Informed Consent and Inclusion/Exclusion	X							
Urine Pregnancy Test <small>*females of child bearing potential only</small>	X							
Randomization	X							
Medical/Dental History	X							
X-rays (if none have been taken in the past two years)	X							
Oral Examination	X			X	X	X	X	X
Pain Visual Analog Scale (VAS)	X	X	X	X	X	X	X	X
Clinic Assessments*	X				X	X	X	X
Intraoral Photographs	X	X ~	X	X	X	X	X	X
Dental Impressions	X							
Tissue Harvest Biopsy ~		X ~						
Graft Placement			X ∞					
Graft Biopsy						X		
Laser Doppler Flowmetry (LDF)					X	X	X	X
Laboratory Evaluations +						X		
Assess Adverse Events		X	X	X	X	X	X	X
Follow-up phone calls will occur at 9 and 12 months post-grafting.								

\*Clinic assessments may include: PPD, CAL, BOP, Mobility, keratinization, graft contracture, graft color, wound healing index,

~Harvest biopsy will be performed only on subjects randomized to the experimental EVPOME arm of the study

+Laboratory evaluations include: histology, immunohistochemistry

∞At this time the POM graft will be harvested from the donor palatal site and grafted to the recipient site

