#### 6.2.3 **Visit 3: Baseline: Intraoral Grafting of EVPOME or POM Grafts**

Grafts will be applied as determined by the randomization schedule. Group 1 subjects will undergo intraoral grafting of EVPOME and Group 2 subjects will receive POM that will be harvested at this time from the donor site, palate. For Group 1 subjects, before release of the EVPOME for grafting from the CTML, glucose utilization will be measured and determined as percent of glucose utilized by the EVPOME during the final days of laboratory incubation. Gram stain analysis will be performed on culture media that the EVPOME was grown in during the final day of incubation. Preliminary results of in-process sampling to determine the sterility (aerobic, anaerobic, and fungal cultures) of the product will

3/28/2017

be reviewed. Results of in-process mycoplasma testing will be reviewed. Analysis of in-process sampling for endotoxin will also be reviewed. If the device fabrication is unsuccessful, the subject will be given the opportunity to have a second palatal or retromandibular trigone (location is at the discretion of the principal investigator and the surgeon) biopsy taken for production of another EVPOME device.

Every effort will be made to maintain contact with the subject for safety data should the subject decline a second biopsy and withdraw from the study to pursue standard of care treatment. It is important to note that in our completed Phase I clinical trial we did not have to abort any procedure because of in-processing difficulties in not achieving our release criteria of passing the sterility tests and satisfying glucose consumption over the last 24 hours. Samples of spent media that the EVPOME was grown in may be stored and analyzed for proteins or other cell secretions in order to better understand graft success or failure.

EVPOME and POM grafts will be sutured and assessed to assure they are immobile. Subjects will be given standard post-operative instructions which may include analgesics and antibiotics per standard of care.

Intraoral photographs will also be taken at this time. A maxillary stent will be placed at this time for the POM subjects.

A visual analog scale of pain will be taken at this time for both group I and II and subjects will also be questioned about any adverse events.

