## 10.4 Adverse Experience Reporting

Adverse Events (AEs) other than routine, mild and expected experiences, either observed by the Investigator or one of his/her medical collaborators, or reported by the subject, will be documented. These AEs will be followed until the event is resolved, until the event is deemed chronic, or until 30 days after the subject's participation in the study has ended.

Expected, routine, mild adverse experiences include: lack of sensation, numbness, swelling, bleeding, and pain associated with the grafting site and lack of adherence of the graft. These adverse experiences will be documented in the medical record.

Any Serious Adverse Event (SAE) that occurs must be reported to the University of Michigan IRB (IRBMED) according to the IRBMED reporting guidelines. Information about all SAEs is collected and recorded on the Serious Adverse Event Report Form. All pertinent medical records and information collected during the treatment and follow-up of the subject should be maintained. The Investigator must assess the SAE relationship to investigational product. All SAEs will be reported to the FDA in compliance with the FDA reporting requirements as found under 21 CFR 312.32. This includes reporting to the FDA all unexpected, fatal or life-threatening adverse events assessed as related to the product by telephone or fax within seven days and the reporting in writing of unexpected serious adverse events assessed as related to the product within 15 days.

Expected Serious Adverse Events include allergic reaction, uncontrollable bleeding and/or pain or an infection requiring hospitalization.

Any death occurring through the end of the study (30 days following the intervention), regardless of the degree of relationship to study, must be reported as a Serious Adverse Event.

The investigator will submit an attribution for the relatedness of the adverse event to the test article or procedure. As far as possible, each AE should be evaluated to determine:

- the severity grade (mild, moderate, severe);
- its relationship to the study investigational product(s);
- its duration (start and end dates or, if ongoing, at final exam);
- action taken; and
- seriousness (yes/no)

The severity grade should be determined by the Investigator using the definitions below:

- Mild: Discomfort noticed but no disruption of normal daily activity;
- Moderate: Discomfort sufficient to reduce or affect normal daily activity; or

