#### 10.5 Data Safety Monitoring Board (DSMB)

A DSMB will be chartered to assure adequate protection of research subjects. The board will review Serious Adverse Events and other pertinent data according to the DSMB charter on a regular basis throughout the study. The DSMB will be comprised of at least three members with expertise in the dental/medical field and experience in the conduct of clinical trials or statistical knowledge. DSMB members will not have any conflicts of interest with the study.

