## 13. STUDY DISCONTINUATION CRITERIA

Stopping Rules for Safety reasons: The Data Safety Monitoring Board (DSMB) will review all Serious Adverse Events (SAEs) and make recommendations regarding the continuation or dis-

continuation of the study, as appropriate. SAEs that may necessitate possible discontinuation include:

- Infection of the graft site reported in 5 experimental subjects. Subjects will be treated with antibiotics and followed until resolution of the infection.
- Complete loss of the experimental graft occurring in 5 subjects
- Severe or excessive oral bleeding in 5 experimental arm subjects requiring transfusion
- Reported uncontrollable oral pain in 5 experimental arm subjects

All subjects will be followed until resolution of the adverse event and will also be contacted 9 and 12 months post-surgery to assess any possible long term safety issues.

Should the study be stopped because of safety concerns, the FDA and IRB will be promptly notified, and a comprehensive safety review will be initiated.

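### Partial graft loss judged routine never reaches the CRF as an event, and no planned analysis reports graft loss by arm

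*Combined protocol and SAP*

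**What the plan says.** **Section 7** lists graft non-adherence with swelling, bruising, numbness and similar experiences that are expected, mild and routine: "lack of adherence of the graft after stent removal will not be considered adverse events". The exception is "unless the magnitude or duration is greater than what is routinely expected". When it applies, "the experience will be considered an adverse event and will be recorded on the Case Report Form". Otherwise the event is noted in the medical record. The same section names graft failure among the possible risks.

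**Section 10.4** repeats the routine listing without restating the exception: "lack of adherence of the graft. These adverse experiences will be documented in the medical record".

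**Section 13** lists, among the SAEs that may lead to discontinuation, "Complete loss of the experimental graft occurring in 5 subjects".

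**Section 10.5** describes oversight: "The board will review Serious Adverse Events and other pertinent data according to the DSMB charter on a regular basis throughout the study".

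**Follow-up assessments.** The footnote to the Section 6.1 schedule reads: "Clinic assessments may include: PPD, CAL, BOP, Mobility, keratinization, graft contracture, graft color, wound healing index". Section 6.3.5 adds KM width, pain and periodontal measures. The one explicit check that the graft is fixed is at surgery (Section 6.2.3): "EVPOME and POM grafts will be sutured and assessed to assure they are immobile".

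**Section 9.2** has KM width as the primary outcome, contracture and the Wound Healing Index as secondary outcomes, and blood flow, graft color, pain, histology and immunohistochemistry as ancillary outcomes. Section 9.5 describes analyses of these efficacy measures and gives no safety analysis.

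**The concern.** Section 1.1 makes safety compared with POM part of the primary objective. Section 6.2.6 says that a pressure dressing stays on for the first 2 weeks and that a graft which fails will do so within 4 weeks. Adherence after stent removal, seen at about Visits 5 and 6, therefore falls in the window in which the protocol expects failures to appear. Yet its default status is that of a non-event.

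The exception turns on what is routinely expected, which is not defined by area, time or assessor. Partial loss that an investigator regards as routine stays out of the safety data. Whether EVPOME grafts detach in part more or less often than POM grafts is basic information for the Phase III trial with larger wounds that this study is meant to inform (Section 1, on the potential to change the standard of care). As written, the plan does not produce that comparison.

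**Working it through.** **1. Where each kind of loss is recorded.**

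| Event | EVPOME arm | POM arm |
|---|---|---|
| Non-adherence judged routine, including partial loss | Medical record only (Sections 7, 10.4) | Medical record only (Sections 7, 10.4) |
| Non-adherence judged greater than routine | AE on the CRF (Section 7) | AE on the CRF (Section 7) |
| Complete loss | SAE, counted toward 5 (Section 13) | Beyond mild and routine, so an AE on the CRF (Section 7); no count |

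The first row is the gap in capture. The third row has no gap in reporting, but the count in Section 13 has no POM counterpart.

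**2. Whether another planned measure identifies a loss.**

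- *KM width* is a distance to the mucogingival line. A low value may follow a loss or poor keratinization.
- *Epithelial coverage* (Section 5.1.8) is a percentage measured at follow-up visits. It may fall after a loss, but Section 9.5 analyzes only histological coverage from the Week 4 biopsy.
- *Wound Healing Index* pools flap dehiscence with edema, erythema and discomfort (Section 9.2.2). A score of 2 or 3 does not say which sign was present.
- *Mobility* in the Section 6.1 footnote stands with the periodontal measures PPD, CAL and BOP, so I do not read it as a graft item.
- *Photographs* could show a loss, but no count is planned from them.
- *Contracture* is the closest measure and is worked through next.

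**3. Contracture.** Inputs from Section 9.5, Aim 2: POM mean 25%, SD 13%, 30 per arm, difference to exclude 11 points.

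The plan's figures reproduce:

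- Standard error = 13 × √(2/30) = 3.36 (stated as about 3.4).
- Margin = 1.96 × 3.36 = 6.58 (stated as 6.6).
- Probability that the 95% interval lies within ±11 when the true difference is 0 = 2Φ(11/3.36 − 1.96) − 1 = 0.81 (stated as 80%).

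The score is 100 × (1 − final area / Day 0 area). Two different grafts, each with 75% of the Day 0 area left:

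- Fully adherent, shrunk by 25%: 100 × (1 − 0.75) = 25.
- 25% of the area sloughed, the rest unshrunken: 100 × (1 − 0.75) = 25.

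The score cannot separate partial loss from shrinkage.

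For complete loss, zero area scores 100. If k of 30 grafts are lost and the rest average 25%, the arm mean rises by k × (100 − 25)/30 = 2.5k points. One loss gives a mean of 27.5%, the same as 30 adherent grafts that each shrank by 27.5%. A comparison of means reflects the loss but does not count it.

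**4. Precision of a loss rate by arm.** Newcombe 95% intervals for the risk difference, 30 per arm:

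- No losses in either arm: the Wilson upper limit for 0/30 is 1.96²/(30 + 1.96²) = 3.84/33.84 = 11.4%, so the interval is ±11.4 points.
- Half lost in each arm (15/30 against 15/30, the upper extreme and not an expectation): Wilson limits 33.2% and 66.8%, half-width 16.8, so the interval is ±√2 × 16.8 = ±23.8 points.

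**The case against.** The strongest reply is that serious cases are already covered. The carve-out is limited to mild and routine experiences and ends when an event exceeds that. Complete loss of an EVPOME graft is an SAE under Section 13, and complete loss of a POM graft can hardly be called mild. The DSMB may see other pertinent data besides SAEs. All of this stands.

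Two stronger readings are therefore tempting but unsupported. A reader might infer that complete losses can disappear into the medical record. Read together, Sections 7 and 13 say otherwise. A reader might also infer that the count of 5 in Section 13 would often be missed. That needs a true loss rate and a share of complete losses wrongly called routine, and the documents give neither. Reaching 5 also prompts DSMB review and is not an automatic stop.

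A second reply is that contracture, coverage and the Wound Healing Index are already collected at Visits 5 to 8 and would show trouble. They may reflect a loss, but for the reasons in the working they do not identify one.

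A third reply is that the CRFs, the Manual of Procedures and the DSMB charter are not part of the documents, so a graft-status field or a working definition may exist there. That is possible. It would not supply the missing analysis by arm, and the rule in Section 7 would still keep routine non-adherence from being an adverse event.

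**Conclusion.** The point holds in a limited form and should be fixed. Partial non-adherence judged routine does not reach the CRF as an event in either arm. The only planned graft-loss count covers one arm. No outcome or analysis in Section 9 reports graft loss for either arm, although safety against POM is in the primary objective.

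The number of cases affected cannot be estimated, because the documents give no rate of partial or complete loss. The arithmetic shows only that contracture is not a substitute: equal scores for partial loss and shrinkage, and 2.5 points on the arm mean per complete loss. The latter assumes that a lost graft is entered as zero area and that the others average the plan's 25%. Nothing here shows that a primary or secondary conclusion would change. The issue is the completeness of the safety comparison and what Phase III can learn from it.

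**What to change.** 1. **CRF item.** Whatever the AE classification, record graft status for every subject in both arms at Visits 5 to 8:
   - fully adherent;
   - partial loss: any detached, necrotic or sloughed graft area, with the estimated percent of the Day 0 area;
   - complete loss: graft tissue clinically absent, detached or necrotic over the whole recipient site. An indistinct border alone does not qualify, because a well-integrated graft may blend with its surroundings.
2. **Sections 7 and 10.4.** Keep on the routine list only minor non-adherence with no loss of graft tissue.
3. **Section 13.** Take the graft-loss count from this item.
4. **Section 9.5.** Report n/N per arm for partial and for complete loss, through Week 4 and through Week 24, with the risk difference and a 95% confidence interval (Newcombe). Label the table descriptive, with no test.

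The cost is one CRF item, two short text edits and one table. Both arms already have an oral examination and contracture measurement at Visits 5 to 8, so no visit or procedure is added. The downsides are slightly more data entry and wide intervals at 30 per arm. The new item is still a clinical judgement, but it is made against a stated definition and recorded for everyone.

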## 8. CRITERIA FOR INTERVENTION DISCONTINUATION

Subjects who are diagnosed with HIV, cancer requiring radiation therapy, etc. will be discontinued from the study.

Those subjects who are discontinued will be asked to return for a final End of Study subject visit as described in Visit 8 study procedures.

## 9. STATISTICAL CONSIDERATIONS

### 9.1 General Design Issues

This is a randomized, parallel-group (autogenous *ex vivo* produced oral mucosa equivalent (EVPOME) vs. palatal oral mucosa (POM)) safety and efficacy study in subjects requiring additional keratinized oral mucosa for dental rehabilitation. The primary hypothesis is that EVPOME is an equivalent intraoral grafting material when compared to POM in regards to keratinized tissue and graft contracture, but is superior to POM in regards to pain, color rendition, and microvessel infiltration.

The comparison will be done using primary efficacy measures of enhanced keratinization, and secondary measures of graft contracture and wound healing index, and ancillary measures of increased microvessel ingrowth. Clinical assessments will include postoperative pain. Intraoral photographs will be done at screening and at biopsy, 2, 4, 8, and 24 weeks after intra-oral grafting. Tissue biopsy will be conducted at week 4 and laser Doppler flowmetry at weeks 2, 4, 8, and 24. Primary assessment time will be at week 4, and final assessments for all subjects will be at week 24.

Subjects will be screened until we have the necessary 60 enrolled. It is likely there will be 4 screened subjects to 1 enrolled subject. All subjects will undergo informed consent prior to any screening procedures. It is expected that it will take 2.5 years to successfully enroll 60 patients. Subjects will be recruited through the Patient Admitting and Emergency Services (PAES) clinic in the U-M School of Dentistry in conjunction with MCOHR. All new patients are routed through PAES and assigned to specialty or

undergraduate clinics. Most patients do not return to the PAES clinic, so we are not likely to have redundancy. PAES had 13,100 visits in 2003. It is estimated that 40% of the western population is missing 1 or more teeth (50% to be restored with implants for our purposes). Approximately 1/3 of them are in need of soft tissue oral mucosa grafts which is a very common procedure. This will give us a population from which to draw approximately 865 new patients per year. Of this group we need to recruit 60 subjects over two years from a potential pool of 1,730 patients. With an estimated enrollment of 1 out of 4 screened patients, we should have a pool of over 400 patients per year from which to select 30 subjects. Subjects will be recruited by full-time faculty members in the Department of Periodontics at the U-M School of Dentistry.

